An anonymized copy on CD ROM (present in each observation book) of each morphological evaluation until progression (even if beyond 6 months) (MRI) is to be made. The copies will be sent to the CRGA of the FFCD for centralized review .

For the translational study, perform a cone beam CT acquisition or a hepatic CT scan without injection at the time of the 1^{ère} HEC.

For the clinical study, if possible, perform a cone beam CT acquisition at each HEC to assess the quality of the chemoembolization.

VII.3 Post-treatment monitoring beyond 6 months after inclusion:

After the end of chemoembolization treatment, patients will be followed according to TNCD recommendations:

Clinical and biological evaluation every 3 months for the first year and then every 6 months for 1 year:

- Clinical examination (weight, WHO)
- Biological tests: liver tests (ASAT, ALAT, GGT, bilirubinemia, albuminemia, TP)
- Marker : AFP

Morphological assessment:

- Chest CT scan without injection, every 6 months for 2 years
- Hepatic MRI (or CT scan) - liver ultrasound by a trained operator alternating every 3 months for 2 years

Monitoring data will be collected in the observation book during this 2-year period.

VIII. STOP PROCESSING THE STUDY

The processing of the study will be stopped in case of:

- Investigator's decision
- Major toxicity requiring discontinuation of treatment
- Serious or unexpected event requiring discontinuation of protocol treatment
- Progression of the disease
- Patient refusal or withdrawal of consent
- Death of the patient

In all cases of treatment discontinuation, the patient remains in the analysis for intention-to-treat and overall survival, and for 30 days after the last study treatment for toxicity.

There is no exclusion period for a subsequent therapeutic trial.

IX. TRANSLATIONAL STUDY

Only patients who have signed their translational-biological informed consent will be collected. Rationale for the study (see Appendix 15).

Blood sampling for VEGF determination

- 4 sampling times:

After the 1^{ière} HEC at D0, D1, D2 and D3

- Samples :

At each sampling time (4 times), collect 2 x 7 ml EDTA tubes of blood.

Centrifuge the blood tubes at room temperature at 1000 g for 15 minutes.

Collect the plasma to be distributed in a minimum of 4 cryotubes (minimum 1 mL per cryotube).

Identify the cryotubes with the patient's initials + inclusion number in the study, the sampling times.

Freeze the 2 plasma cryotubes at -20°C then at -80°C.

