- The rate of patients in objective response** (complete response or partial response) at 6 months according to mRECIST criteria and evaluated by the investigator.
- The rate of patients in objective response** (complete response or partial response) at 6 months according to EASL criteria assessed by the investigator and in centralized review.

- Time to treatment failure

It is defined as the time interval between the date of inclusion and the date of protocol treatment failure. Death, progression, and any discontinuation of protocol treatment (regardless of cause) are considered treatment failures.

Patients alive without failure will be censored at the date of the last 6-month morphological evaluation.

- The best response according to the mRECIST criteria

- Progression-free survival

It is defined as the time interval between the date of inclusion and the date of 1st progression according to mRECIST criteria (assessed in centralized review) or death (regardless of cause).

Patients living without progression will be censored at the date of last news.

- Overall survival

It is defined as the time interval between the date of inclusion and the date of death (regardless of cause) or the date of last news for living patients.

- Tolerance of the treatment

Toxicities will be evaluated by the NCI-CTC v4.0 criteria. They will be described according to their grade in terms of number of toxicities and number of patients who experienced the toxicity.

- Quality of life (QLQ-C30 questionnaires and its HCC18 module specific to HCC)

XII.3 Calculation of the number of subjects needed

The assumptions are:

- H0: A proportion of patients with an objective response at 6 months of 25% or less is not acceptable
- H1: A proportion of patients with an objective response at 6 months of more than 25% would demonstrate the effectiveness of the treatment. A rate of 40% is hoped for.

Using a 2-stage Fleming design (Fleming, 1982) with a one-sided alpha risk of 5% and power of 90%, it is necessary to include **86 treated and evaluable patients**.

At the 1^{ère} stage: 43 patients will be included

- If 10 or fewer patients have an objective response, the trial will be stopped for futility (H1 rejection)
- If 18 or more patients have an objective response, the trial will be stopped for efficacy (rejection of H0)

If not, we will go to 2^{ème} step including 43 additional patients

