#### **4.2 Treatment arms**

[figure not shown]
There is a single study treatment arm consisting of 1 to 4 sessions of chemoembolization (sessions spaced 6 weeks +/- 1) with idarubicin-loaded microbeads (100-300 µm) (10 mg).

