### **7.4.3 Time to treatment failure**

#### **7.4.3.1 Definition**

It is defined as the time between the date of inclusion and the date of definitive cessation of treatment or death (whatever the cause). Patients without definitive treatment discontinuation and not deceased will be censored at the date of their last HEC.

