#### **7.4.3.2 Evaluation**

The time scale considered is the month.

Time to treatment failure will be plotted using the Kaplan Meier estimator. Median times and rates at different temporalities will be calculated, along with their 95% confidence intervals.

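### Time to treatment failure counts failures without a time limit but censors failure-free patients at an early date, so later Kaplan-Meier rates are biased low

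*Protocol*

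**What the plan says.** Protocol XII.2.2 measures TTF from inclusion. On events: "Death, progression, and any discontinuation of protocol treatment (regardless of cause) are considered treatment failures". No upper time limit is given. On censoring: "Patients alive without failure will be censored at the date of the last 6-month morphological evaluation".

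SAP 7.4.3.1 (Time to treatment failure) redefines the event as definitive cessation of treatment or death from any cause, again with no time limit. Its censoring rule is: "Patients without definitive treatment discontinuation and not deceased will be censored at the date of their last HEC". SAP 7.4.3.2 then states: "Time to treatment failure will be plotted using the Kaplan Meier estimator", with medians, rates at several times and 95% confidence intervals.

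Failures after month 6 will be known. Protocol VII.3 follows patients for two years and adds: "Monitoring data will be collected in the observation book during this 2-year period". Protocol VII.2 and X ask for an anonymized copy "of each morphological evaluation until progression (even if beyond 6 months) (MRI) is to be made".

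The two neighbouring endpoints are handled differently. PFS is censored at last news (protocol) or last evaluation (SAP), and overall survival at last news.

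**The concern.** Kaplan-Meier assumes that a patient's removal from the risk set carries no information about that patient's later outcome. Here the removal date is chosen after the outcome is known.

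Protocol rule: a patient who progresses at month 11 is at risk until month 11 and is then an event. A patient followed failure-free to month 20 is removed at month 6.

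SAP rule: take two patients with no recorded definitive cessation. One dies at month 15 and is an event then. The other is alive at month 24 and is removed at the last HEC.

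Beyond the censoring dates the risk set contains only patients already known to fail. The rates reported there are then too low, and if any failure falls after the last censoring date the curve ends at exactly zero. The medians, rates and intervals planned in SAP 7.4.3.2 would not describe time to failure. Each rule has this defect on its own, so copying the protocol's censoring sentence into the SAP would not remove it.

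**Working it through.** The documents state no figure for TTF, so there is none to reproduce. The failure rates and lengths of follow-up below are assumptions.

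**Inputs from the documents.** Event and censoring rules: protocol XII.2.2 and SAP 7.4.3.1. Follow-up: two years of monitoring (protocol VII.3). Sessions: "There is a single study treatment arm consisting of 1 to 4 sessions of chemoembolization (sessions spaced 6 weeks +/- 1" week (SAP 4.2), starting at most 2 weeks after inclusion (protocol IV). A single HEC can therefore put the SAP censoring date within 2 weeks of inclusion. Four sessions on schedule put it at about 2 + 3 × 6 = 20 weeks, or 140 / 30.4375 = 4.6 months. Evaluable patients: 44 (SAP 4.6.1).

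**Protocol rule, closed form.** Let failure times be exponential with median m, so S(t) = 2^(−t/m), and follow everyone for 24 months. After month 6 only patients with 6 < T ≤ 24 remain at risk, so

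KM(t) = S(6) × [S(t) − S(24)] / [S(6) − S(24)].

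For m = 12: S(6) = 0.707, S(12) = 0.500, S(24) = 0.250.
- KM(12) = 0.707 × 0.250 / 0.457 = 0.387, against 0.500.
- KM(24) = 0, against 0.250.
- The estimated median solves S(t) = 0.250 + 0.5 × 0.457 / 0.707 = 0.573, giving 9.6 months against 12.

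| True median (months) | 12-month rate: true / protocol rule | 24-month rate: true / protocol rule | Estimated median (months) |
|---|---|---|---|
| 6 | 0.250 / 0.214 | 0.063 / 0 | 6.0 |
| 12 | 0.500 / 0.387 | 0.250 / 0 | 9.6 |
| 18 | 0.630 / 0.466 | 0.397 / 0 | 11.3 |
| 24 | 0.707 / 0.511 | 0.500 / 0 | 12.2 |

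**Sensitivity to follow-up.** If follow-up is uniform from 12 to 30 months, replace S(24) by the mean of S over that range. For m = 12 this is [S(12) − S(30)] / (18 × ln 2 / 12) = 0.323 / 1.040 = 0.311. Then KM(12) = 0.707 × (0.500 − 0.311) / (0.707 − 0.311) = 0.34, against 0.50.

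**At the trial's size.** In 1,000 simulated trials of 44 patients with m = 12 and 24 months of follow-up, the mean 12-month rate was 0.387 under the protocol rule and 0.501 with censoring at the end of follow-up. The protocol-rule curve ended at zero in every replicate; the ordinary curve ended at 0.253 on average.

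**SAP rule, hand check.** Suppose no cessation is recorded, median survival is 18 months and follow-up is 24 months. If all last HECs fell at 0.5 months: S(0.5) = 0.981, and KM(12) = 0.981 × (0.630 − 0.397) / (0.981 − 0.397) = 0.39. If all fell at 4.7 months: 0.834 × 0.233 / 0.438 = 0.44. The true rate is 0.63.

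**SAP rule, simulation.** 44 patients, 1 to 4 sessions equally likely, last HEC at 0.5 to 4.7 months, cessation dates uniform over 0.5 to 6 months, 24 months of follow-up. Entries are 12-month rates, SAP rule / ordinary censoring.

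| Patients assigned a cessation date | Median survival 18 months | Median survival 30 months |
|---|---|---|
| 0% | 0.424 / 0.630 | 0.481 / 0.755 |
| 20% | 0.309 / 0.505 | 0.329 / 0.609 |
| 50% | 0.168 / 0.316 | 0.160 / 0.379 |
| 90% | 0.025 / 0.062 | 0.021 / 0.076 |
| 100% | 0 / 0 | 0 / 0 |

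The gap is 21 to 27 points with none recorded, much the same at 20%, about 4 to 6 points at 90%, and nil at 100%.

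**The case against.** **A 6-month horizon was intended.** The endpoint concerns protocol treatment. The visit schedule separates the treatment period, ending with the 6-month visit, from later follow-up, and VII.3 calls the later period post-treatment. If failures also stop counting at the 6-month scan, the protocol rule is ordinary administrative censoring and is valid. This is a fair reading, but it rests on the schedule: no sentence stops events at month 6. It does not help the SAP, which counts death at any time.

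**The translated phrase may mean the last six-monthly evaluation.** That would largely remove the protocol bias. Elsewhere, however, the protocol uses 6 months for the single assessment dated from inclusion. Again the SAP rule is untouched.

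**The SAP supersedes the protocol, and nearly every patient will have stopped treatment.** With at most four sessions, most patients should have finished by the final analysis. If completion is recorded as definitive cessation, few or none are censored. This stands as a limit on size. But the SAP does not define definitive cessation, and its censoring sentence expects living patients without it.

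**The median may not move.** Correct under the protocol rule when the true median is about 6 months or less. Under the SAP rule with 70% of cessations recorded (placed 5 weeks after the last HEC, an assumption), the median is 4.2 months either way, although the 12-month rate still drops from 21% to 6%.

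**TTF is descriptive.** True: no test or decision depends on it.

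**Conclusion.** The point holds for a secondary endpoint. As written, both rules make continued presence in the risk set depend on later failure, so Kaplan-Meier rates after the censoring date are biased low. The curve reaches zero at the last failure, provided some failure occurs after the last censoring date; two years of follow-up make that very likely.

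The size depends on failure rates that the documents do not give. For true medians of 12 to 24 months with 24 months of follow-up, the protocol rule understates the 12-month rate by 11 to 20 points. Those medians presuppose that simply finishing the sessions is not a failure. The SAP rule distorts earlier, because last-HEC dates can fall within weeks of inclusion, but its bias vanishes if every patient has a recorded cessation.

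A reader might infer three stronger things that the documents do not support:
- That the median is always too low. Under the protocol rule the curve up to month 6 is essentially unaffected.
- That the curve must collapse whatever the plan meant. With a 6-month limit on events, or cessation recorded for everyone, the censoring creates no bias.
- That the efficacy conclusion is weakened. The primary endpoint and its decision rule do not use TTF.

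**What to change.** Use one horizon for events and censoring in both protocol XII.2.2 and SAP 7.4.3.1, and state whether planned completion of the sessions counts as failure. The event lists should be aligned in the same edit, because the SAP omits progression. Two forms work:

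- (a) Count failures throughout follow-up and censor patients without failure at their last failure-free evaluation or last news, in line with PFS and overall survival. With a true median of 12 months and 24 months of follow-up, this recovers the 12-month rate of 0.50 and the median of 12.
- (b) Count only failures up to the 6-month evaluation, censor everyone still failure-free on that date, and report no rates beyond 6 months. In simulation with the same median this gave a 6-month rate of 0.706 against a true 0.707.

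The cost is about one sentence in each document, using data already collected. Option (b) gives up any estimate after month 6.

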### 4.6.2 Second stage: final analysis

In view of the results of the interim analysis and the discontinuation of the study for efficacy, the final analysis will be performed with a last news date for each patient after 01/01/2017.

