## **6.2 Agreements concerning dates and durations**

Time since inclusion will be defined as the time elapsed since the day of inclusion, the day of inclusion being considered as day 1.

Time since start of treatment will be defined as the time elapsed since the day of the first treatment course, the day of the first treatment course being considered as day 1.

As a result, durations are calculated using the following rule, for example for the time elapsed between death and inclusion: day of death - day of inclusion **+ 1**.

The day preceding the day of inclusion (*resp.* the day preceding the day of treatment) will be considered as day -1 (day 0 does not exist).

The date of last news will default to the date of the last examination/monitoring performed.

The following conversion rules will be used to convert numbers of days into numbers of months or years:  
1 month = 30.4375 days; 1 year = 365.25 days.

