### **7.4.2 Progression-free survival**

#### **7.4.2.1 Definition**

It is defined as the time between the date of inclusion and the date of first progression assessed by centralized review, or the date of death (whatever the cause). Patients alive without progression will be censored at the date of last evaluation.

Patients for whom no evaluation is available will be censored at inclusion date + 1 day.

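### The SAP changes the PFS censoring date from last news to last evaluation without saying so, and its rule for patients with no evaluation is not limited to living patients

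*Protocol*

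**What the plan says.** Both documents measure PFS from inclusion to the first progression on centralized review, or death from any cause. They differ on patients who have had neither.

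- Protocol XII.2.2: "Patients living without progression will be censored at the date of last news".
- SAP 7.4.2.1: "Patients alive without progression will be censored at the date of last evaluation". It then adds: "Patients for whom no evaluation is available will be censored at inclusion date + 1 day".

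Two further SAP passages bear on how far apart these dates can be. Section 6.2 says: "The date of last news will default to the date of the last examination/monitoring performed". Section 4.6.2 says that "the final analysis will be performed with a last news date for each patient after 01/01/2017"; it sets no matching requirement for imaging. Protocol VII.3 schedules clinical and laboratory visits after month 6 separately from imaging, and alternates liver MRI (or CT) with ultrasound every 3 months, so an MRI or CT falls due about every 6 months.

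**The concern.** Progression can only be found on a scan that goes to central review. A patient who stops being scanned but is still seen in clinic cannot have a progression recorded, yet under the protocol rule stays in the risk set as progression-free until last contact. That raises the curve. Because last news must be brought up to date for every patient at the final analysis and imaging need not be, the gap between the two dates could be real. The SAP moves to a different rule but does not say that it departs from the protocol, so a reader of the report cannot tell from the two texts whether the change was deliberate.

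The second problem lies within the SAP. Death from any cause is an event, but the sentence on patients with no evaluation carries no restriction to living patients. Someone who dies before the first scan satisfies both statements, and no order of precedence is given. Applied literally, the censoring sentence removes exactly the earliest events. In a single-arm trial there is no control arm in which such a bias could cancel.

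**Working it through.** **What the plan gives.** There is no PFS assumption, event count or power in either document, so no PFS figure can be reproduced. The only sample-size figure concerns the 6-month response rate. It reproduces exactly (43 + 43 patients, bounds 10, 18 and 29: exact alpha 4.74%, power 90.2%) and does not involve PFS. Everything below is illustration on stated assumptions, except the direct arithmetic in step 1.

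**Step 1: deaths before any scan.** Inputs: 46 patients included (SAP 4.6.1); *k* = number who die in the first month before any scan (assumed). The first MRI is due 4 to 6 weeks after the first session, so assume no other event in month 1.

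- Deaths counted as events: 1-month PFS = 1 − *k*/46. For *k* = 1, 2, 4 this is 45/46 = 97.8%, 44/46 = 95.7%, 42/46 = 91.3%.
- Deaths censored at inclusion + 1 day: 1-month PFS = 100% in every case.

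The effect carries forward. If *S* is the 6-month PFS of the other 46 − *k* patients, the estimate is *S*(1 − *k*/46) with events and *S* with censoring, a rise of *S* × *k*/46. Assume exponential PFS with a median of 6 to 15 months, so *S* runs from 2^(−6/6) = 0.50 to 2^(−6/15) = 0.76. The rise is then 1.1-1.7 points for *k* = 1, 2.2-3.3 for *k* = 2 and 4.3-6.6 for *k* = 4.

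On dating: SAP 6.2 has "the day of inclusion being considered as day 1", so inclusion + 1 day is day 2, a duration of 2/30.4375 = 0.066 month.

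**Step 2: last news against last evaluation.** Assumptions, none from the documents except the approximate scan schedule: exponential time to progression, median 8 months; exponential time to death, median 24 months; follow-up uniform over 6 to 28 months; MRI at 1.5, 3, 4.5, 6, 12, 18 and 24 months; permanent imaging dropout of 0 to 30% per visit after month 6, with vital status still followed.

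True PFS: the hazards add, ln 2 × (1/8 + 1/24) = ln 2 / 6, so the median is 6 months, 12-month PFS is 2^(−2) = 25.0% and 18-month PFS is 2^(−3) = 12.5%.

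Simulated Kaplan-Meier results (40,000 patients):

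- No imaging dropout: last news 24.9% and last evaluation 24.1% at 12 months; 12.3% and 11.4% at 18 months. The rules differ by about 1 point even here.
- 10-30% dropout, last news: about 2-5 points too high at 12 months; 15.8-21.1% at 18 months, about 3-9 points too high.
- 30% dropout, last evaluation: 10.5% at 18 months, about 2 points too low. Survivors are censored back to their last scan while deaths after that scan still count, so the risk set is too small when those deaths occur.

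Deaths must be in the model. With progression alone (true PFS 35% at 12 months and 21% at 18), last news gives 38-43% and 26-36% at the same dropout rates, and last evaluation looks almost unbiased. Both results arise from omitting a component of the endpoint.

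A second simulation, with 46 patients and 0-30% of them leaving imaging at a random time between 2 and 10 months, points the same way: median PFS 6.3-7.1 months with last news against about 6.1 with last evaluation.

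**Step 3: set against precision.** With 46 patients and true PFS of 25% at 12 months, the standard error without censoring is √(0.25 × 0.75/46) = 6.4 points, a 95% half-width of about 12.5 points. The illustrated bias is smaller than that.

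**The case against.** A reader might infer that the final report could follow either text, leaving the PFS curve undetermined. The documents do not support that. Protocol XII.4 provides for a SAP before the database is frozen. The SAP reports the January 2017 interim analysis, gives the more specific definition, and has the secondary efficacy criteria programmed twice. It is the operative text and already uses the better of the two rules. What remains is an undeclared departure.

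A reader might also infer that an ultrasound visit could serve as the last evaluation. Protocol section X confines the centralized reading to MRI and CT, and SAP 7.4.2.1 ties progression to that reading. Naming the modality only tightens the wording.

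On early deaths, the + 1 day sentence follows one about living patients and can be read as a sub-case of it. The protocol's modified ITT population requires a post-treatment evaluation, which would remove most patients without one. Neither point fully closes the gap. SAP 7.4.2 names no population for PFS, and SAP 5.1.2 treats deaths within 6 months as evaluable, but only for the primary endpoint. It is equally unsupported to infer that early deaths have in fact been lost: the documents report none, and give no reasons for the 2 of 46 patients who were not evaluable.

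Finally, the dropout rates are assumed. The only planning figure is 5% lost to follow-up or not evaluable.

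**Conclusion.** The point holds as a discrepancy of wording with a limited effect. The two documents censor PFS at different dates and the SAP does not say so. The SAP's + 1 day sentence, as worded, conflicts with death as an event.

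The direction is clear: the protocol's rule raises PFS when imaging lapses before contact does, and censoring early deaths raises it too. The size is not known, because neither the number of patients leaving imaging nor the number dying before a scan is given; the figures in the working depend on the assumptions stated there. The SAP's rule is preferable but not unbiased.

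PFS is descriptive, with no hypothesis, threshold or power attached. Nothing here touches the primary endpoint, the sample size or the decision to stop for efficacy.

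**What to change.** In SAP 7.4.2.1:

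1. State that censoring at the last evaluation replaces the last-news rule of protocol XII.2.2, and define the last evaluation as the last MRI or CT assessed under mRECIST.
2. Limit the inclusion + 1 day rule to patients who are alive with no evaluation.
3. State that death is always a PFS event, whether or not a scan was done.
4. Report PFS with last-news censoring as a sensitivity analysis, so that readers can see how far the two rules differ in the actual data.

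The cost is a few sentences and one additional Kaplan-Meier run. No new data are needed.

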If 29 or more patients have an objective response, the treatment is declared effective (rejection of H0)

Taking into account a 5% rate of patients lost to follow-up or not evaluable, **91 patients** will be included. The decision rules will be adapted based on the number of evaluable patients actually included.

XII.4 Statistical analysis plan

A statistical analysis plan will be written prior to freezing the database.

Analysis Populations:

The characteristics of the patients included in the study will be described in strict intention-to-treat (ITT). Efficacy analyses will be performed on a modified intention-to-treat (mITT) basis: all evaluable patients included in the study regardless of eligibility criteria. A patient is considered evaluable if he/she has had at least one chemoembolization and one post-treatment evaluation.

Population evaluable for safety:

The ITT population that received at least one chemoembolization.

Statistical analysis:

The description of the variables will be done using percentages (95% confidence interval) for qualitative variables and using mean (standard deviation) and median (Min-Max) as well as the inter-quartile range (Q1-Q3) for quantitative variables.

The estimation of censored data will be done by the Kaplan Meier (KM) method. Times will be described by medians and rates at different time points with their 95% confidence intervals. The median follow-up time will be calculated using the reverse Kaplan Meir method.

XII.5 Independent Committee

An independent committee composed of 1 clinician / 1 methodologist-statistician / 1 pharmacovigilant expert / 1 radiologist will be set up before the beginning of the trial. It will meet regularly during the course of the study according to the rate of inclusion.

It will have to rule on the declared ADRs. It can also be seized at any time by the Sponsor in case of significant facts on the tolerance (ADRs and AEs) of the treatment.

XIII. JUSTIFICATION OF THE TEST

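### Protocol XII.4 puts overall survival, PFS and time to treatment failure on evaluable patients although they run from inclusion; this conflicts with section VIII on overall survival, and SAP 7.4 names no population to settle it.

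*Protocol*

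**What the plan says.** **Protocol XII.4 (Analysis Populations).** Strict ITT is used to describe patient characteristics. For efficacy: "Efficacy analyses will be performed on a modified intention-to-treat (mITT) basis: all evaluable patients included in the study regardless of eligibility criteria". The set is defined by: "A patient is considered evaluable if he/she has had at least one chemoembolization and one post-treatment evaluation".

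**Protocol XII.2.2.** OS, PFS and time to treatment failure all start at inclusion. For PFS, for example: "It is defined as the time interval between the date of inclusion and the date of 1st progression according to mRECIST criteria" or death.

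**Protocol VIII.** Death is one of the listed reasons for stopping study treatment. In every case of stopping, "the patient remains in the analysis for intention-to-treat and overall survival".

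**SAP 5.1.1 and 5.1.2.** ITT is every included patient. The evaluable set, called CP, is defined for the primary endpoint. Deaths in the first six months count as evaluable failures for that endpoint, but a patient with no imaging at all is non-evaluable.

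**SAP 7.** Populations are labelled for 7.1 and 7.2 (ITT), 7.3 (CP) and 7.5 (tolerance population). Section 7.4, which holds every secondary efficacy endpoint, carries no label. Its PFS definition adds: "Patients for whom no evaluation is available will be censored at inclusion date + 1 day".

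**The concern.** Membership of the mITT set depends on something that happens after the survival clock has started. A patient who dies between inclusion and the evaluation never enters, so the death disappears from both numerator and denominator. The patients who remain contribute a stretch of follow-up in which death was impossible. This is immortal time, and it pushes the curve up.

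The trial has one arm, so no control group carries the same bias. Protocol XIII says that an earlier randomized chemoembolization trial can serve for comparison of efficacy, and XII.1 schedules a 2-year OS analysis. Protocol VI.1 lists death among the expected adverse effects of the procedure, and the window in question is the one just after it.

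The rules also cannot all be followed. A treated patient who dies before any evaluation is removed from OS by XII.4 and kept in it by section VIII.

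**Working it through.** **1. The plan's own figures.** 86 / 0.95 = 90.5, rounded up to 91 included. An exact two-stage binomial calculation (43 + 43; stop at 10 or fewer, or at 18 or more; final bound 29) gives a one-sided alpha of 0.047 at 25% and power of 0.902 at 40%. The design reproduces. The plan gives no figure for the effect of the population rule.

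**2. Length of the guaranteed period.** Treatment starts within 2 weeks of inclusion (protocol IV) and imaging follows 4 to 6 weeks after each session (protocol VII.2). If the evaluation is imaging, the period runs from 0 + 4 = 4 weeks to 2 + 6 = 8 weeks. The protocol does not define a post-treatment evaluation. If a clinical visit counts, the period is shorter.

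**3. Worst case for survival.** SAP 4.6.1 reports 46 included and 44 evaluable, so 2/46 = 4.3% are excluded. Suppose both died before any other event or censoring. Then

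S_ITT(t) = S_evaluable(t) × 44/46, so S_evaluable(t) = S_ITT(t) × 46/44 = S_ITT(t) × 1.045.

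| Evaluable curve reads | All 46 patients | Difference (points) |
|---|---|---|
| 95.0% | 90.9% | 4.1 |
| 80.0% | 76.5% | 3.5 |
| 50.0% | 47.8% | 2.2 |

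An assumed all-patient survival of 40% (not a figure in the documents) would read 0.40 × 1.045 = 41.8%, which is 1.8 points too high. For the median, the evaluable curve stands at 0.5 × 46/44 = 0.523 when the all-patient curve reaches 0.5. Under an exponential curve the ratio of medians is ln(0.5)/ln(0.523) = 1.07, so the apparent median is about 7% too long.

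**4. Best case.** If neither excluded patient was an early death, this mechanism adds nothing.

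**5. Primary endpoint, as a check.** Exact one-sided 95% lower bound = 5% quantile of Beta(x, n − x + 1).
- 22/44 = 50.0%, lower bound 36.8%.
- 22/46 = 47.8%, lower bound 35.0%, counting both excluded patients as failures.

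Both bounds exceed 25%.

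**The case against.** The strongest reply is that the SAP has already narrowed the rule. It drops the mITT label, defines the evaluable set for the primary endpoint only, and treats deaths within six months as evaluable. If that rule was applied at the interim analysis, the two non-evaluable patients were probably not early deaths. The secondary endpoints are also descriptive: at an assumed 40% with 44 patients, the approximate 95% half-width is 1.96 × √(0.4 × 0.6/44) = 14 points, against a worst-case bias of 1.8.

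Most of this stands as to size. It does not settle the plan. The early-death rule is worded for the primary endpoint, and it clashes with the no-imaging rule beside it for a patient who dies before any scan. Section 7.4 remains unlabelled.

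Some stronger readings are tempting but not supported:
- *That mITT is the only population stated for survival.* Section VIII states another for OS, and the SAP restricts its evaluable set to the primary endpoint.
- *That everyone kept is event-free until the evaluation.* Only survival is guaranteed. A patient can stop treatment, which the protocol counts as a failure, and still be imaged later. Progression seen at the first evaluation is also kept.
- *That the PFS censoring rule proves ITT was meant.* It implies a set wider than CP, but the tolerance population would also fit.
- *That section VIII contradicts XII.4 equally for all three endpoints.* It names OS and concerns patients who stop treatment. For PFS and time to failure the clash rests on its general ITT wording, and patients never treated are not clearly covered.
- *That the planned 91/86 = 1.058 sets the size.* The trial stopped for efficacy after 46 inclusions.

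**Conclusion.** The concern holds as a conflict between stated rules. Protocol XII.4, taken literally, conditions OS, PFS and time to treatment failure on surviving to an evaluation and contradicts section VIII on OS. SAP 7.4 does not choose between them.

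A reader might go further and infer that the trial's survival curves are in fact biased upward. The documents do not support that: they give no reason for the two exclusions and do not show which population was used. The overstatement lies between nothing and a factor of 1.045. The upper end assumes that both excluded patients died before anyone else had an event or was censored. The decision on the primary endpoint does not change. The point deserves correction because the change is cheap and the survival results of a single-arm trial are likely to be set beside outside figures.

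**What to change.** - State in SAP 7.4 that OS, PFS and time to treatment failure are analysed in the ITT population of SAP 5.1.1. Keep CP for the response rates.
- Align protocol XII.4 with section VIII, so that the evaluable restriction no longer reaches these three endpoints.
- Add a censoring rule for time to failure in living patients who were included but never had a chemoembolization. The SAP censors at the last session, a date they do not have. Inclusion date plus one day, as for PFS, is one option.
- Make clear that day-one censoring in PFS applies only to living patients with no evaluation, so that a death before any evaluation stays an event.

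The cost is wording only, with no new data. Survival estimates may become slightly less favourable.
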